#### 13.1.1. Relationship to Study Treatment

A qualified investigator must make the determination of relationship to the investigational product for each AE. The Investigator should decide whether, in his or her medical judgment, there is a reasonable possibility that the event may have been caused by the study treatment.

Causality Category	Description
Unlikely related	
A clinical event, including laboratory test abnormality, with a temporal relationship to study treatment administration which makes a causal relationship improbable or if other drugs, chemicals or underlying disease provide more plausible explanations.
 
While temporal sequence may be an important factor in determining causality: i.e., whether the observed reaction or event began after the study treatment, it may well be that the surgery, anesthesia, a concurrent medical condition or concomitant medications administered during or after surgery were more likely than not to be responsible for the AE. The investigator should use clinical judgment to evaluate the evidence and determine whether there is a reasonable possibility that study treatment actually caused the AE or whether based upon the evidence it is more likely that something else is responsible. If the former, choose “possibly related” and if the latter, “unlikely related.”

	For the purpose of this protocol, the term “unlikely related” will be considered an AE not related to study treatment.
Possibly related	A clinical event, including laboratory test abnormality, with a temporal relationship to study treatment administration, which also may be explained by concurrent disease or other drugs or chemicals. In such cases, if the investigator using clinical judgment is unable to rule out a reasonable possibility that study treatment was partly responsible, then choose “possibly related.” For the purpose of this protocol, an event that has possible relationship to study treatment will be defined as a “Suspected Adverse Drug Reaction”.
Probably related	A clinical event, including laboratory test abnormality, with a temporal relationship to study treatment administration, in which the investigator has determined that the event is unlikely to be attributed to other factors. For the purpose of this protocol, an event that has probable relationship to study treatment will be defined as an “Adverse Drug Reaction”.

### 13.1.2. Adverse Event Reporting

All AEs must be entered on the AE CRF, regardless of causality or severity. AEs include new AEs, worsening baseline conditions, clinically significant laboratory findings, disease-related signs and symptoms that were not present at baseline, and any events or findings that the Investigator feels are clinically significant.

Disease-related signs and symptoms that are present at baseline should not be recorded as AEs unless they worsen in severity or increase in frequency.

Information collected concerning AEs will include the following:

- Name of the event
- Onset date
- Resolution date
- Severity (i.e., mild, moderate, severe or potentially life-threatening)
- Relationship to study treatment
- Action and outcome
- Seriousness of event

All SAEs will be documented and followed from the time the subject has signed the ICF until 29 (+/- 3 days), or, if necessary, Day 36 after the completion of surgery. All SAEs and non-serious AEs will be documented and followed from the time of administration of study treatment until Day 29 or, if necessary, Day 36 after the completion of surgery. AEs that occur between Screening and the administration of study medication should be considered medical history and added to the subject's medical record, unless the AE is due to a study-related procedure (such as phlebotomy), in which case it will be recorded as a non-treatment emergent AE. AEs that have been designated as possibly related to study treatment will be followed until resolution or stabilization.

### **13.1.3. Serious Adverse Event (SAE)**

An SAE or reaction is any adverse drug experience occurring at any dose that results in any of the following outcomes:

- Death
- Is life-threatening (at the time of the event)
- Requires subject hospitalization or prolongation of existing hospitalization,
- Results in persistent or significant disability/incapacity
- Is a congenital anomaly/birth defect (in an offspring)
- An Important medical event that may not result in death, be life-threatening, or require hospitalization may be considered an SAE when, based upon appropriate medical judgment, the event may jeopardize the subject and/or may require medical or surgical intervention to prevent one of the outcomes listed in this definition.

All AEs requiring hospitalization or prolongation of a pre-existing hospitalization should be reported as SAEs unless they occur greater than 14 days after the Day 29 visit, or 21 days after early termination AND are not considered to be study treatment-related by the Investigator.

Hospitalizations meeting the following criteria will not be reported as an SAE but must be recorded on the appropriate CRF: study specified hospitalization, short-term administrative hospitalization for procedures, tests or treatments of conditions that would not otherwise constitute an SAE, elective hospitalizations.

#### **13.1.3.1. Serious Adverse Event Reporting**

Serious AEs must be reported to the Sponsor or designee within 24 hours of knowledge of the event. All SAEs that occur while a subject is receiving study treatment and within 14 days following the study completion visit (or 21 days following an ET if applicable) are reportable within 24 hours. During this follow-up period beyond study completion or after an ET, only

those SAEs considered to be possibly related to study treatment should be reported within 24 hours.

The procedure for reporting an SAE is as follows:

- All SAEs must be reported immediately (within 24 hours of discovery) by email to the CRO Medical Monitor or designee. Calls related to SAEs should first be directed to the CRO Medical Monitor or designee.

CRO Medical Monitor: [name], CPI

24/7 Emergency contact: [contact]

SAE Reporting email: [[contact]](mailto:[contact])

- The Sponsor's Medical Monitor is available for questions about safety-related issues: [name] JD MBA; [contact] or [[contact]](mailto:[contact]).
- The initial report should include all information known at the time of the report (additional information can be reported as discovered). Do not delay the initial reporting in order to obtain resolution or follow-up information.
- The site will enter into the electronic database (or fax, if the database cannot be accessed for any reason) an SAE report, or similar form, that includes the following information, as available:
  - Subject ID
  - Basic demographic information (age, gender, weight)
  - Outcomes attributed to the event (death, life-threatening hospitalization [new or prolonged], disability, congenital anomaly, required medical intervention to prevent permanent impairment/damage, etc.)
  - Onset date and severity of the event
  - Brief description of the event including frequency and severity of symptoms leading to diagnosis
  - List of relevant test results and laboratory data
  - Any other relevant history
  - Whether the study treatment was discontinued
  - Investigator's assessment of causality

The CRO Medical Monitor or another representative of the Sponsor may contact the Investigator to request additional information regarding the event or to confirm information. All SAEs will be entered on the AE CRF. The same nomenclature should be used on both the SAE report and the AE CRF. The Investigator is responsible for the complete and timely reporting of all SAEs to the Sponsor (or designee), reporting pertinent follow-up information on the SAE, and notifying the appropriate IRB of the occurrence of and details surrounding the event. In the event there is a question as to whether the AE is serious, the event should be reported.

## **13.2. Pregnancy**

If a female subject becomes pregnant at any time during the study, the Investigator must notify the CRO Medical Monitor or designee within 48 hours of learning about the pregnancy. The Investigator will be required to follow the subject through the pregnancy term, and report to the CRO Medical Monitor or designee the course of the pregnancy, including perinatal or neonatal outcome. Information on the status of the mother and the child will be forwarded to the CRO Medical Monitor or designee. Any premature termination of the pregnancy will also be reported on this form. Although pregnancy occurring in a clinical study is not considered to be an SAE, any pregnancy complication or elective termination of a pregnancy for medical reasons will be recorded as an AE and will be followed as such. A spontaneous abortion is considered to be an SAE.

## 14. DATA QUALITY ASSURANCE

This study will be conducted under Good Clinical Practice (GCP) and all applicable regulatory requirements. To ensure compliance, the Sponsor or designee may conduct a quality assurance audit, as outlined in [Section 14.2](#).

Actions to ensure the accuracy and reliability of data include the selection of qualified investigators and appropriate study centers; the review of protocol procedures with the Investigator and study personnel prior to study start; the design of suitable source documents with appropriate instructions for use (where applicable); the internal audit of source data according to GCP and internal procedures to ensure their accuracy, completeness, and verifiability; as well as the periodic site monitoring by the Sponsor. The Sponsor or designee will review source documents for accuracy and completeness during on-site monitoring visits and after their return to the Sponsor; any discrepancies will be resolved with the Investigator, as appropriate.

Significant and/or repeated non-compliance will be investigated and remedial action instituted when appropriate. Failure to comply with remedial actions may result in investigational site termination and regulatory authority notification.

### 14.1. Data Collection

Source documents include, but are not limited to, original documents, data and records such as hospital/medical records (including electronic health records), clinic charts, lab results, participant diaries, data recorded in automated instruments, microfilm or magnetic media, and pharmacy records, etc. This study will use electronic data capture (EDC). At a minimum, all data required by the protocol should have supporting source documentation for entries in the EDC system.

All CRFs will be completed by the site staff prior to review by the Sponsor's monitor or designated representative. The Sponsor's monitor or designated representative will review all source records on-site and compare them to the data collected on the CRF. All entries, corrections, and alterations will be made by the Investigator or other authorized study personnel. All data entries will be verified for accuracy and correctness by independent monitors. The electronic data capture system maintains a full audit trail.

### 14.2. Study Auditing and Monitoring

Monitoring of the study site (including, but not limited to, reviewing CRFs for accuracy and completeness) will be performed by the Sponsor's designated monitor(s). The extent, nature, and frequency of on-site visits will be based on such considerations as the study objectives and/or

endpoints, the purpose of the study, study design complexity, and enrollment rate. By signing the protocol, the Investigator agrees that, within local regulatory restrictions and institutional and ethical considerations, authorized representatives of the Sponsor, a regulatory authority, and/or an IRB may visit the site to perform audits or inspections, including the drug storage area, study treatment stocks, drug accountability records, participant charts and source documents, and other records related to study conduct. The purpose of the Sponsor audit or inspection is to systematically and independently examine all study-related activities and documents to determine whether the study-related activities were conducted, and data recorded, analyzed, and accurately reported according to the protocol, the site's standard operating procedures, GCP guidelines of the ICH, and any applicable regulatory requirements. The Investigator should contact the Sponsor immediately if contacted by a regulatory agency regarding an inspection.

## 15. STATISTICAL METHODS

### 15.1. Statistical and Analytical Plans

This section describes the statistical methods to be used to analyze the efficacy and safety. The final analysis will be documented in a formal Statistical Analysis Plan (SAP) that will be finalized before database lock. The SAP will include details on how variables will be derived, how missing data will be handled, and how data will be presented as well as the details on statistical methods to be used for safety and efficacy analyses. The final clinical study report will discuss deviations from the SAP, if any.

### 15.2. Sample Size Justification

In the previously completed Phase 1 ascending dose safety study in bunionectomy (CA-008 vs. placebo), the mean difference between CA-008 (all dose groups combined) and placebo for the  $AUC_{24 \text{ to } 96h}$  was -120. The standard deviation (SD) estimates for the six treatment arms in this study ranged from 70 to 190 with a median SD of 108. For the primary endpoint ( $AUC_{0 \text{ to } 96h}$ ), the true treatment difference between the 4.2 mg CA-008 group and the placebo group is assumed to be equal to -100 and the assumed true SD is equal to 130. For these assumptions, and based on the use of a two-sided, two-sample comparison of means at the  $\alpha=0.05$  level of significance, a sample size of 36 subjects per arm will provide 90% power. Thus, the planned total sample size is 144 subjects.

### 15.3. Analysis Populations

The following three analysis populations are planned for this study:

- The Safety Population will include all subjects who received at least part of a dose of study treatment.
- The PK Population will include all subjects who receive a full dose of study treatment and complete at least all PK assessments through the T6h timepoint. Subjects who fail to complete these PK assessments will be replaced.
- The modified ITT (mITT) Population will include all subjects who receive a full dose of study treatment and complete the first 3 pain assessments (through T2h).

Subjects who elect to discontinue study participation during the inpatient phase of the study, will be asked to continue with assessments through T96h if they have not elected to withdraw from all aspects of study participation. Subjects who elect to discontinue participation after discharge from the inpatient unit but prior to D8 (W1) will be considered to have terminated as of the date of their election, however they will be asked to return to the site to reassess the surgical site for wound healing.

All safety assessments and baseline characteristics will be summarized using the Safety Population. PK and efficacy analyses will be performed using the PK and mITT Populations, respectively. All summaries will be grouped by the actual treatment received. Each active dose cohort will be presented separately, along with a combined active dose group.

Inpatient Study Completer will be defined as those subjects who complete the assessments through T96h. Outpatient Study Completer will be defined as those subjects who complete the assessments through D29±2 (W4).

Membership in the analysis populations will be determined before unblinding.

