4 SUBJECT POPULATIONS

4.1 Analysis Populations

Six analysis populations are defined as follows:

- **Intent-to-treat (ITT)** population: all subjects who are randomized. Subjects will be analyzed according to the treatment they were randomized to.
- **Modified intent-to-treat (mITT)** population: all subjects who receive a full dose of study treatment and complete the first 3 pain assessments (through T2h). Subjects will be analyzed according to the treatment they were randomized to.
- **In patient study completer (Inpatient CP)**: all subjects who receive a full dose of study treatment and complete the inpatient assessment period (through T96h). Subjects will be analyzed according to the treatment they were randomized to.
- **Study Completers (CP)**: all subjects who receive a full dose of study treatment and complete the entire study period through D29±2/W4. Subjects will be analyzed according to the treatment they were randomized to.
- **Safety** Population will include all randomized subjects who received any amount of study drug. subjects will be analyzed by treatment group according to the actual treatment received, i.e., “as treated”.
- **Pharmacokinetic (PK)** population: All randomized participants who received a full dose of study drug and complete all PK assessments through the first 6 hours (T6h) time point. Note, subjects who fail to complete these PK assessments will be replaced.

Analysis populations will be determined before study unblinding.

The primary and secondary efficacy analyses will be performed using mITT population. Efficacy analyses will also be carried out using ITT, Inpatient CP and/or CP populations for selected endpoints as appropriate. Baseline characteristics will be summarized using ITT population and safety endpoints will be summarized using Safety population. PK summaries will be presented using the PK population.

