7.4 Efficacy Endpoints

CONFIDENTIAL

Efficacy will be evaluated using the numeric rating scale of pain intensity (NRS) scores (at rest and with ambulation), PGE, IGE, Rescue Use and Healthcare utilization. A variety of time-specific summed pain intensity assessments (area under the curve (AUC) for pain intensity) will be calculated using NRS to compare treatment difference between CA-008 and placebo group.

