7.4.3 Other Efficacy Endpoints

- AUC of subject's NRS will be examined over various time periods: $AUC_{0 \text{ to } 6h}$, $AUC_{0 \text{ to } 12h}$, $AUC_{0 \text{ to } 24h}$, $AUC_{0 \text{ to } 120h}$, $AUC_{0 \text{ to } w1}$ (walking), $AUC_{0 \text{ to } w2}$, $AUC_{0 \text{ to } w2}$ (walking), $AUC_{12 \text{ to } 24h}$, $AUC_{24 \text{ to } 48h}$, $AUC_{24 \text{ to } 72h}$, $AUC_{24 \text{ to } 96h}$, $AUC_{96 \text{ to } 120h}$, $AUC_{96h \text{ to } w1}$, $AUC_{24h \text{ to } w1}$ (walking), $AUC_{96h \text{ to } w2}$, $AUC_{96h \text{ to } w2}$ (walking).
- Time-specific ("milestone") mean pain intensity NRS at 6, 12, 24, 28, 72, 96, 120, 144, and 168 hours
- Time-specific ("milestone") mean pain intensity NRS by site at 6, 12, 24, 28, 72, 96, 120, 144, and 168 hours
- OC over following time periods: $OC_{24 \text{ to } 48h}$, $OC_{24 \text{ to } 72h}$, $OC_{24 \text{ to } 96h}$.
- OF over following time periods: $OF_{24 \text{ to } 96h}$, $OF_{96h \text{ to } w1}$, $OF_{96h \text{ to } w2}$.
- Time to first use of rescue medication ($TTFR_{\text{after } T0}$) and first use after 24 hours ($TTFR_{\text{after } T24h}$). For the analysis of time to use of rescue medication, only OPIOID rescue medication will be considered,
- Analgesic consumption (AC) from T96h to W1 ($AC_{96h \text{ to } W1}$) and $AC_{96h \text{ to } W2}$.
- Patient global evaluation (PGE) comparing the percentage of subjects reporting (poor or fair) versus (good or excellent) responses and the percentage reporting each category of response at W1, W2 and W4.
- Investigator's global evaluation (IGE) comparing the percentage of those reporting (poor or fair) versus (good or excellent) responses and the percentage reporting each category at W1, W2 and W4.
- Number and percentage of subjects who drop out due to an AE or lack of efficacy (LOE) during the inpatient period: $LOE_{24 \text{ to } 96h}$, $LOE_{0 \text{ to } 96h}$.

- Health care utilization after discharge from the inpatient unit: HCU_{96h to W2} and HCU_{96h to W4}. (Not included in this SAP)

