7.5.9 Percent of Subjects Taking Rescue / Use of Rescue Medication over Time

Subjects will be counted as having taken rescue on any particular day based on the rescue medication page of the eCRF and the at home rescue diary. If additional medications, other than the study rescue medications, appear on the concomitant medications page and can be identified as having been taken for bunion pain, those medications will also be counted.

The proportion of subjects taking rescue will be summarized for each study day through Day 15.

In addition, the proportion of subjects taking any rescue medication during the following periods: 0-96 hours, 24-48 hours, 24-72 hours, 24-96 hours, 96h to Week 1 and 96h to Week 2 and overall will be summarized and will be analyzed using Fisher's exact tests.

Separate summaries for opioid and non-opioid rescue use will be presented if sufficient data are present in the groups.

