Table 14.2.2.5.1	mITT Population	Summary of NRS at Rest and with Walking by Time Point (WOCF)
Table 14.2.2.5.2	mITT Population	Summary of NRS at Rest and with Walking by Time Point and by Site (WOCF)

Table 14.2.2.6	mITT Population	Summary of NRS at Rest and with Walking by Time Point (LOCF)
Table 14.2.2.7.1	mITT Population	Summary of NRS at Rest and with Walking by Time Point (Observed Data, No Imputation for Drop Out)
Table 14.2.2.7.2	mITT Population	Summary of NRS at Rest and with Walking by Time Point and by Site (Observed Data, No Imputation for Drop Out)
Table 14.2.3	mITT Population	Logistic Analysis of Proportion of Subjects who are Opioid Free Outcome (Key Secondary and Exploratory Analyses)
Table 14.2.4.1.1	mITT Population	ANOVA Analysis of Opioid Consumption (in Morphine equivalents) (Key Secondary and Exploratory Analyses)
Table 14.2.4.1.2	mITT Population	ANOVA Analysis of Opioid Consumption by Site (in Morphine equivalents) (Key Secondary and Exploratory Analyses)
Table 14.2.4.2.1	mITT Population – Subjects Who Took Any Opioid Medication	ANOVA Analysis Mean Daily Opioid Consumption (in Morphine Equivalents)
Table 14.2.4.2.2	mITT Population – Subjects Who Took Any Opioid Medication	ANOVA Analysis Mean Daily Opioid Consumption by Site (in Morphine Equivalents)
Table 14.2.5.1	Safety Population	Kaplan-Meier Analysis of Time to First Use of Opioid Rescue Medication
Table 14.2.5.2	Safety Population – Subjects Who Took First Opioid Rescue Medication Prior to 60 Minutes Post-Dose	Kaplan-Meier Analysis of Time to Second Use of Opioid Rescue Medication
Table 14.2.6	mITT Population	CMH and Fishers Analysis of Patient Global Evaluation (PGE)
Table 14.2.7	mITT Population	CMH and Fishers Analysis of Investigator Global Evaluation (IGE)
Table 14.2.8	mITT Population	Fishers Analysis of Proportion of Drop Out During the Inpatient Period
Table 14.2.9.1	Safety Population	Fishers Analysis of Percent of Subjects using Rescue Medication Over Time
Table 14.2.9.2	Safety Population	Summary of Percent of Subjects Using Rescue Medication by Day
Table 14.3.1.1	Safety Population	Overall Summary of Treatment-Emergent Adverse Events (TEAEs)
Table 14.3.1.2	Safety Population	Summary of TEAEs by System Organ Class and Preferred Term

Table 14.3.1.3	Safety Population	Summary of Treatment Related TEAEs by System Organ Class and Preferred Term
Table 14.3.1.4	Safety Population	Summary of SAEs by System Organ Class and Preferred Term

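### The rescue-use efficacy displays sit on the as-treated Safety population instead of mITT as randomised; only the Fisher table (14.2.9.1) is affected inferentially, and the effect may be nil

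*Protocol*

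**What the plan says.** **Status of the endpoints.** Protocol 12.6.1.3 and SAP 7.4.3 list time to first rescue among the other efficacy endpoints, and the SAP limits it to opioids: "For the analysis of time to use of rescue medication, only OPIOID rescue medication will be considered". SAP 7.4 includes rescue use among the measures by which efficacy is judged ("PGE, IGE, Rescue Use and Healthcare utilization"). SAP 7.5.9 applies Fisher's exact test to "the proportion of subjects taking any rescue medication during the following periods", with 0-96 h and 24-96 h among those periods.

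**Population rules.** Protocol 15.3 states "PK and efficacy analyses will be performed using the PK and mITT Populations, respectively", then "All summaries will be grouped by the actual treatment received"; the synopsis repeats the second sentence. SAP 4.1 groups ITT, mITT and both completer sets as randomised. For the Safety population, which needs only some amount of study drug, it says "subjects will be analyzed by treatment group according to the actual treatment received".

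**Table and figure list.** SAP 14.1.1 assigns the Safety population to "Kaplan-Meier Analysis of Time to First Use of Opioid Rescue Medication" (Table 14.2.5.1) and "Fishers Analysis of Percent of Subjects using Rescue Medication Over Time" (Table 14.2.9.1), and also to Tables 14.2.5.2 and 14.2.9.2. SAP 14.1.2 does the same for Figures 14.2.3.1 to 14.2.3.3. The opioid-free table (14.2.3) and the opioid-consumption tables are on mITT. The SAP gives no reason for the difference, and its Section 12 lists no change from the Protocol.

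**The concern.** Two things are at stake. First, a between-arm p-value from as-treated groups no longer rests on the randomisation alone, because a subject given the wrong vial is counted in an arm to which chance did not assign that subject. Secondly, the opioid-free rate over 0-96 h is the first key secondary endpoint, analysed on mITT as randomised. Percent using rescue over the same window is nearly its mirror image, but is analysed on Safety as treated. A reader of the report could find two accounts of almost the same outcome with different denominators and different arm membership, and no explanation.

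**Working it through.** **The plan's own figure.** The only design figure nearby is the sample size, which this point does not dispute. With difference 100, SD 130, two-sided alpha 0.05 and 90% power:

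n = 2 × (1.960 + 1.282)² × 130² / 100² = 2 × 10.51 × 1.69 = 35.5, so 36 per arm.

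Power at 36 per arm is 0.904 by the normal approximation. The stated figure reproduces, and nothing below changes it.

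**Which displays carry a test.**

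| Display | Content | Population | Planned between-arm test |
|---|---|---|---|
| Tables 14.2.5.1, 14.2.5.2; Figures 14.2.3.1 to 14.2.3.3 | Time to first or second opioid rescue | Safety | None named (SAP 7.5.5: Kaplan-Meier plots, medians and CIs) |
| Table 14.2.9.1 | Percent using rescue by period | Safety | Fisher's exact (SAP 7.5.9) |
| Table 14.2.9.2 | Percent using rescue by day | Safety | None |
| Table 14.2.3 | Opioid free | mITT | Logistic regression (SAP 7.5.3) |

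The other tested efficacy tables (AUC, opioid consumption, PGE, IGE, inpatient dropout) are on mITT or completer sets, all as randomised. Table 14.2.9.1 is the exception.

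**How close the two outcomes are.** Protocol 9.1.3 allows no NSAID or acetaminophen after the intraoperative doses until T96h, so protocol rescue in hospital is oxycodone. For 0-96 h and 24-96 h, percent using rescue is therefore close to 1 minus the opioid-free proportion. It is not exact: SAP 7.5.9 adds other medication taken for bunion pain, whereas SAP 7.5.3 adds any identifiable opioid. After discharge, OTC analgesics can count as rescue but do not count against opioid-free status, and the two separate.

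**How the populations can differ.** mITT requires a full dose and the first three pain scores (through T2h); Safety requires any dose. So they differ in membership if a subject is partially dosed or misses an early score, and in grouping if a subject receives the wrong treatment. With none of these, the two sets coincide.

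**Size.** The documents give no rescue rates and no misdosing counts, so the counts here are assumed. Take opioid users as 33/36 on placebo and 26/36 on 4.2 mg.

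| Situation | Placebo | 4.2 mg | Fisher p |
|---|---|---|---|
| No discrepancy | 33/36 | 26/36 | 0.063 |
| One user randomised to 4.2 mg received placebo: as treated | 34/37 | 25/35 | 0.033 |
| One 4.2 mg user in Safety but not mITT: mITT table (Safety stays at 0.063) | 33/36 | 25/35 | 0.035 |
| One placebo user in Safety but not mITT: mITT table | 32/35 | 26/36 | 0.063 |

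In the second row the arm rates move little, from 91.7% to 91.9% and from 72.2% to 71.4%. The p-value crosses 0.05 because the assumed counts start near it. From assumed counts of 34/36 and 27/36, the same move takes p from 0.046 to 0.022, with no crossing.

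**The case against.** The strongest reply is that this is a reporting choice of little consequence. Protocol 12.6.2 lists concomitant medications among the safety endpoints and SAP Table 14.1.4 summarises them on Safety, so tabulating rescue on the same set is defensible. Percent using rescue is not in the endpoint lists of Protocol 12.6.1.3 or SAP 7.4.3. SAP 4.1 ties only primary and secondary efficacy analyses to mITT, and Protocol 15.1 leaves analysis details to the SAP. mITT itself removes treated subjects after randomisation, so it is not the full randomised set either. A single dose given by study staff leaves little room for misdosing.

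Much of this stands as a limit on size. It does not explain an efficacy-numbered table with between-arm p-values on an as-treated set, since Protocol 15.3 sends efficacy to mITT without exempting minor endpoints.

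Three stronger readings are tempting, and the documents support none of them:

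- A reader might infer that the opioid-free key secondary, or the primary analysis, loses its randomised grouping. Under SAP 4.1 and 14.1 both are on mITT as randomised. The Protocol sentence, read literally, would group the opioid-free analysis as treated too and so create no mismatch; the mismatch arises from SAP 4.1 together with the table list.
- A reader might infer that comparisons of time to first rescue are compromised. No between-arm test of it is planned.
- A reader might infer that a common population would make the two rescue analyses agree. Fisher's test and a four-level logistic model can still give different p-values, and the definitions differ slightly.

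**Conclusion.** The inconsistency is real: seven rescue displays in the efficacy series are on the as-treated Safety population, against Protocol 15.3 and out of line with the SAP's other tested efficacy tables. The consequence for inference is confined to Table 14.2.9.1, an unadjusted analysis outside the gated hierarchy. The overlap with the opioid-free outcome holds for the inpatient windows only.

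The effect is nil if every treated subject received the assigned treatment in full and gave the first three pain scores. Otherwise one subject can be enough to put the two populations on opposite sides of 0.05, but that rests on assumed counts near the threshold. Sample size, power, and the primary and key secondary tests are unchanged. Severity is minor; this is a cheap improvement.

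**What to change.** In SAP 14.1, set Tables 14.2.5.1, 14.2.5.2, 14.2.9.1 and 14.2.9.2 and Figures 14.2.3.1 to 14.2.3.3 to mITT, grouped as randomised. Keep a Safety version as supportive if wanted. In Protocol 15.3 and the synopsis, limit the sentence on grouping by treatment received to safety and PK summaries, so that it agrees with SAP 4.1. Do both before unblinding, so that no one can ask whether the population was chosen on the results.

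The cost is a change of labels on four tables and three figures, and one sentence in two places. The one downside is that mITT drops treated subjects without a full dose or without the first three pain scores, some of whom may have rescue data. A supportive Safety or ITT table covers them.
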